#### **Adherence to treatment (Morisky Questionnaire).**

The MMAS-8 rating scale consists of eight items with a “Yes” = 0 and “No” = 1 rating system for the first seven items and a 5-point response for the last item. Items will be added in order to obtain a score.

- The score will be described continuously and categorically (0 = high adherence, 1-2 = average adherence,  $\geq 3$  = low adherence) at each measurement time.

#### **Quality of life (FACT-leu version 4 – Specific questionnaire on leukemia)**

- Scores obtained based on the FACT-leu questionnaire will be calculated at each measurement time according to rules on calculation provided in Annex 3.5.
- The gain in quality of life, defined by the difference between the best score recorded for a patient and his baseline score, will be calculated.

#### **Describing treatment modalities for bosutinib under real life conditions of use**

- Dosage: mean dosage prescribed at time of initiation and average dosage during treatment.
- Change to dose and reasons: percent of patients with dose reduction/percent of patients with a dose increase and if applicable, description of the reason .
- Maintenance of dose intensity and relative dose intensity (defined as the result of the ratio of the dose received over the expected dose): percent of patients with a dose intensity/relative dose intensity maintained over time and at different measurement times.
- Temporary discontinuation of treatment: percent of patients with temporary discontinuation of treatment and description of the reason; cumulative duration of temporary discontinuations.

- Permanent discontinuation of treatment: percent of patients with a permanent discontinuation of treatment and description of reason for discontinuation.
- Duration of treatment: duration of initiation up to discontinuation of treatment will be calculated for all causes of discontinuation combined and by cause of discontinuation (Kaplan-Meier survival curves).

**Cumulative response to treatment (hematological, cytogenetic and molecular results) and duration up to response and response time**

**Response rate for patients in CP, AP or BP according to treatment line:**

- Cumulative hematological response:
  - o percent of patients presenting with a CHR during treatment with bosutinib (*best response according to the participating doctor's judgement*)
  - o percent of patients presenting with a PHR during treatment with bosutinib (*best response according to the participating doctor's judgement*)
- Cumulative cytogenetic response:
  - o percent of patients presenting with CCyR during treatment with bosutinib (*best response according to the participating doctor's judgement*)
  - o percent of patients presenting with MCyR during treatment with bosutinib (*best response according to the participating doctor's judgement*)
  - o percent of patients presenting with PCyR during treatment with bosutinib (*best response according to the participating doctor's judgement*)
  - o percent of patients presenting with mCyR during treatment with bosutinib (*best response according to the participating doctor's judgement*)
- Cumulative molecular response:
  - o percent of patients presenting with CMR (MR^4; MR4.5; MR^5) during treatment with bosutinib (*best response according to the participating doctor's judgement*)
  - o percent of patients presenting with an MMR (MR^3) during treatment with bosutinib (*best response according to the participating doctor's judgement*)

**Suboptimal response (after dose escalation or without dose escalation due to ongoing toxicities):**

- Patient with chronic phase CML, refer to ELN guidelines 2013.
- Patient with accelerated phase or blast phase CML, loss of all hematological response.

**Median time to response:**

For each response (hematological, cytogenetic, molecular), the median time to occurrence of response will correspond to the median duration between date of initiation of bosutinib and the first date of response as defined in the aforementioned (Kaplan Meier method).

**Median duration of response**

For each response (hematological, cytogenetic, molecular), the median duration of response will correspond to the median duration between first date of response as defined in the aforementioned and the confirmed loss of response, the progression of disease or death of the patient (Kaplan Meier method).

**Response according to mean dose received**

- For each response (hematological, cytogenetic, molecular), the percent of patients with a response according to mean dose received in period of follow-up up to response will be described (stratification based on dose)
- Logistic regression on each response (hematological, cytogenetic, molecular) according to mean dose received in the period of follow-up up to the (quantitative) response

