### 9.3. Variables

Patients will be identified indirectly via a unique number in the study (the centre no., patient no. pair).

The following “patient” data will be collected in the setting of the study at the usual consultation of patients in the centres.

Data	Role	Source
Compliance with criteria for inclusion and non-inclusion	Baseline characteristics	Inclusion visit
Demographic characteristics (year of birth, gender, weight, height, ECOG performance status)	Baseline characteristics	Inclusion visit
Diagnosis of CML (date of diagnosis, phase of CML at time of diagnosis, tests performed for diagnosis)	Baseline characteristics	Inclusion visit
Transcription of BCR-ABL gene at time of diagnosis	Baseline characteristics	Inclusion visit
Previous treatments of CML (type, dose, dosage, duration of previous treatment)	Baseline characteristics	Inclusion visit
Best response to previous treatments	Baseline characteristics	Inclusion visit
Reasons for change of previous treatments (if discontinuation for toxicity, description of the AE: type and grade)	Baseline characteristics	Inclusion visit
Phase of CML in the estimate of the participating doctor, at time of initiation of treatment with bosutinib	Baseline characteristics	Inclusion visit Follow-up visit
Evolution of mutational profile of BCR-ABL gene at time of initiation of treatment with bosutinib	Baseline characteristics	Inclusion visit Follow-up visit
Concomitant treatments at time of inclusion in the setting of management of CML	Baseline characteristics	Inclusion visit
Biological and hematological assessment data	Baseline characteristics Evaluation end point	Inclusion visit Follow-up visit
Hematological, cytogenetic and molecular response at time of inclusion and results	Baseline characteristics	Inclusion visit
Description of initiation of treatment with bosutinib (date of initiation, dose, dosage)	Baseline characteristics	Inclusion visit
Change to concomitant treatments in the setting of management of CML	Evaluation end point	Inclusion visit Follow-up visit
Description of treatment with bosutinib (changes to dose or dosage, temporary or permanent discontinuations of treatment)	Evaluation end point	Follow-up visit
Safety in treatment with bosutinib	Evaluation end point	Follow-up visit
Management of toxicities related to bosutinib (concomitant treatments, additional corrective medical measures)	Evaluation end point	Follow-up visit

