#### **Modelling**

- Linear mixed model

PFIZER CONFIDENTIAL

CT24WI-GL02-RF01.1.0 *Model of non-interventional study protocol for study on collection of principal data*

15/08/2018

Page 34 of 79

Linear mixed models for repeated data will be used in the setting of analysis of continuous repeated data (longitudinal analyses). This approach will enable (1) to take into account all data from patients, and (2) to estimate at each measurement time the mean parameter on all of the patients, adjusted to the phase of CML and to treatment line. It will apply to analysis of biological and hematological parameters. The outcome in comparison to baseline (M0) will be estimated by appropriate contrasts.

- Logistical regression

Multivariate logistical regressions (binary variables) or polynomial (multi-categorical variables) will make it possible to estimate the association of qualitative parameters studied (e.g. response) and of explanatory variables (without notion of time). All models used will be adjusted to potential confounding factors or changes to effect.

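### The secondary dose–response analysis averages dose up to the response itself, so it can show a dose association where none exists

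*Protocol*

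**What the plan says.** Protocol section 9.7.3, under Response according to mean dose received, plans two analyses for each of the hematological, cytogenetic and molecular responses. One gives the percentage responding "according to mean dose received in period of follow-up up to response will be described (stratification based on dose"). The other is a model: "Logistic regression on each response (hematological, cytogenetic, molecular) according to mean dose received in the period of follow-up up to the (quantitative) response". Section 8.2 lists response by dose within a secondary objective.

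Section 9.7.1 (Modelling) says that logistic regressions relate the outcome to "explanatory variables (without notion of time") and promises adjustment for confounders. No averaging window is given for patients who never respond. Dose is expected to move both ways: the treatment-modalities part of 9.7.3 tabulates "percent of patients with dose reduction/percent of patients with a dose increase", together with temporary and permanent stops.

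The response rates count, for example, "percent of patients presenting with CCyR during treatment with bosutinib", taking the best response as judged by the doctor. Time to response is the "median duration between date of initiation of bosutinib and the first date of response". Section 9.2.1 admits intolerant as well as resistant patients. Section 9.3 lists "Hematological, cytogenetic and molecular response at time of inclusion and results" as a baseline characteristic.

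**The concern.** An exposure should be fixed before the outcome, or at least measured over a window that does not depend on it. Here the outcome closes the window. A responder is averaged over a short early stretch of treatment; a non-responder is averaged over a longer one that includes later dose changes. Two patients with identical dosing then get different exposure values only because one responded. Adjusting for covariates does not repair this, and a model that ignores time cannot.

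The result could be read as evidence about dosing, and because the sign of the bias depends on the mix of dose changes, it cannot be corrected by judgement afterwards.

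A related weakness concerns who counts as a responder. A patient who switches for intolerance may already hold the response in question. The definitions as worded do not exclude that patient, who would have a time to response near zero and no dose window to average over.

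**Working it through.** **1. The plan's own figure.** Section 9.5 gives a 95% half-width of at most 10% for a 50% rate with about 100 patients (Wald). 1.96 × √(0.5 × 0.5 / 100) = 9.80%, so it reproduces. This point does not affect it. The protocol gives no figure for the dose analysis.

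**2. The mechanism by hand** (illustrative dose values). Take relative dose 1.0 with one change at month 4, and 36 months of follow-up (section 9.1).
- Response at or before month 4: mean dose 1.00.
- No response, reduced to 0.8: (4 × 1.0 + 32 × 0.8) / 36 = 29.6 / 36 = 0.82.
- No response, increased to 1.2: (4 × 1.0 + 32 × 1.2) / 36 = 42.4 / 36 = 1.18.
- No response, treatment stopped at month 4: 1.00, so no gap.

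The same process can make higher dose look helpful, harmful or neutral.

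**3. Simulation with no dose effect.** From the protocol: N = 100, 36 months, 5% type 1 error (taken as two-sided). Assumed: 30%, 50% or 70% respond, at about 6.5 months on average; at most one dose change per patient, at a median of 4 months, to 0.6–0.8 or to 1.2 of the starting dose; non-responders averaged to month 36. There were 2,000 studies per row and response rate.

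| Dose changes | False positives at 30 / 50 / 70% response | Median OR per SD of mean dose |
|---|---|---|
| 50% reduced | 73 / 84 / 80% | 1.99 / 1.91 / 1.83 |
| 20% reduced | 7 / 28 / 33% | 1.51 / 1.44 / 1.37 |
| 50% reduced, 20% increased | 28 / 42 / 44% | 1.41 / 1.46 / 1.48 |
| 20% reduced, 20% increased | 2.5 / 6 / 11% | 1.09 / 1.09 / 1.10 |
| 30% increased only | 42 / 58 / 55% | 0.59 / 0.62 / 0.65 |

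Adding 20% of patients already in response at start to the 50%-reduced, 50%-response case raises 84% to 96%.

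**4. Sensitivity to the assumptions.** A second null model steps dose from 100% to 80% to 60% at 0.03–0.10 per month, with 30% or 50% responding.
- Reductions only, every non-responder averaged to month 36: OR per 10% higher mean dose 1.84–2.33, false positives 63–100% over two runs.
- 30% of patients increased instead: OR 1.19–1.25, false positives 12–38%.
- Window stopped at discontinuation, median 18 months: OR 1.06–1.24, false positives 2–17%. Across medians of 12–24 months in a separate run: OR 1.04–1.55, false positives 3–73%.

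**5. A fixed window.** Using dose in the first 3 months and later response among patients not yet responding, the scenarios in step 3 give 0.1–3.8% false positives and a median OR per SD of 0.97–1.05. A 6-month landmark in the model of step 4 gives OR 0.99–1.01.

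**6. Responses present at start.** Let b be the share already in response at bosutinib start and q the response rate among the rest. If all are counted, the reported rate is b + (1 − b)q, which exceeds q by b(1 − q). With b = 20% and q = 40% (both assumed): 0.20 + 0.80 × 0.40 = 52%, an excess of 12 points. With b = 0 the excess is zero.

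**The case against.** The study is single-arm and descriptive, with no test hypothesis, and its primary objectives concern related adverse events and discontinuations. Section 9.7.3 leaves detail of the secondary analyses to the SAP, and section 9.7 lets the SAP change the protocol's plans. This limits the severity. It does not remove the dose point, because the protocol already fixes exposure, outcome and model; a SAP that only elaborates them keeps the flaw.

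A reader might infer that the analysis will show a large false benefit of higher dose, with an odds ratio near 2 and significance in most studies. The documents do not support that. Those figures need reductions only and averaging to month 36. At 0.03–0.10 per month, 1 − exp(−0.03 × 36) = 66% to 1 − exp(−0.10 × 36) = 97% of patients would have a reduction, a rate found nowhere in the protocol. The plan also expects increases, and section 7.3 cites about 20% stopping for adverse events in Study 200. This objection stands.

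A reader might also infer that response rates are inflated by a known amount, for instance a CCyR of 32–65%. That range takes an assumed 10–40% already in CCyR and treats the 24–41% from Study 200 as newly gained, which section 7.3 does not say. The protocol never states that carried-over responses count; it only fails to exclude them, and the SAP could settle the evaluable set.

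**Conclusion.** The dose analysis should be fixed, as a matter for one secondary objective. The protocol's stated exposure depends on the outcome, and that alone can create an association between mean dose and response. The direction is unknown in advance. The size depends on the frequency and mix of dose changes and on time on drug, none of which the protocol gives. Over the assumed scenarios at n = 100, false positives run from about the nominal 5% to over 90%, and the odds ratio per 10% higher mean dose from below 1 to about 2.3. All of these figures take non-responders' windows to end at treatment stop or month 36, which the protocol does not specify.

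The baseline-response point is a clarification. The wording admits responses already held at start, the excess would be b(1 − q), and it cannot be sized from the documents.

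**What to change.** Replace both analyses under Response according to mean dose received with one of these:
- a landmark analysis: mean dose in a fixed early window (for example the first 3 or 6 months) among patients on treatment and not yet in that response, against later response;
- a Cox model for time to response with dose as a time-dependent covariate.

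For each response level, compute the rate, time to response and dose analysis among patients without that response at bosutinib start, and report maintained responses separately. Section 9.2.1 allows bosutinib to start up to a month before the inclusion visit, so baseline status should be the last result before the first dose.

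The cost is analysis wording, with no new visits or patients. The dose change can be made in the SAP, since section 9.7 requires an amendment only for major changes to the primary criteria. The landmark loses responders before the cut-off, and the response rates have smaller denominators. Neither model removes confounding where poor response itself prompts a dose change, so the result should still be reported as descriptive.

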**Progression**

Defined as passage from the chronic phase to the accelerated phase or to blast phase. This progression must be validated by two consecutive evaluations less than one week apart. Patients presenting an increase in leukocyte count in at least one period greater than or equal to one month, with second assay measurement  $> 20 \times 10^9/L$  and confirmed at least one week later. Patients presenting a loss of major hematological response (with hematological confirmation within a time greater than or equal to 2 weeks after loss of initial response) or non-confirmation of major cytogenetic response (with a Ph+ rate increased by 30%).

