DATA ANALYSIS	
All tests will be performed with a type 1 error <math>\alpha = 5\%</math>.
 
A descriptive analysis of qualitative and ordinal variables will consist of the sample size and frequency of each modality with its 95% confidence interval (CI). Quantitative variables will be described for the overall population and for each cohort (chronic phase, accelerated phase, blast phase) of patients analyzed, in terms of sample size, mean and medium, standard deviation (SD), confidence interval, as well as number of missing data.
 
An estimate of progression-free survival (PFS) and of overall survival (OS) will be measured by the Kaplan-Meier method. The survival function <math>S(t)</math> will be the probability that the event of interest (progression or death respectively) does not occur before date <math>t</math>. The percent survival will be estimated and described in each of the cohorts of interest.
 
Data will be evaluated separately for patients presenting with chronic phase, accelerated phase or blast phase Philadelphia chromosome +/- CML and depending on treatment line.
 
Interim analyses will be performed if necessary.

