### **9.1. Study design**

This is a national, observational, descriptive, prospective, multicentre study conducted in metropolitan France in adult patients treated for accelerated or blast phase Philadelphia chromosome positive chronic myeloid leukemia, previously treated with one or more TKIs and for whom imatinib, nilotinib and dasatinib are not considered as appropriate treatments. The study will be conducted in all centres involved in management of CML, i.e. about twenty (20) in expected centres.

[figure not shown]
The study will be offered to the totality of patients who satisfy criteria for inclusion and for non-inclusion up to the end of the inclusion period defined as 4 years. About one hundred

(100) patients included are expected in the study. Therapeutic management of a patient will not be changed by participation in the study and will depend on decisions taken by doctors in agreement with current international recommendations (European Leukemia Net, ELN network [13]) (see paragraph 7.3).

Patients will be followed prospectively over a 3-year period starting with their inclusion in the study. The inclusion visit will be performed at time of inclusion of the patient in the study, after which the patient has been informed and has accepted to participate by signing the consent form. Follow-up visits will be performed after usual consultation, estimated at about every 3 months. No visit or additional examination will be requested by the protocol: modalities for follow-up and treatment will be left up to the entire judgement of the participating doctor. Data will be recorded during the 3 years of the patient's participation, except in case of withdrawal of consent, death of a patient or termination of the study before its planned end.

Total duration of the study is estimated at 7 years with an inclusion period of 4 years and a follow-up period of 3 years (see Figure 1). Throughout the study, at least one monitoring visit per year will be performed.

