#### 9.4.1.3. Long-term follow-up visit

Patients who have permanently discontinued their treatment with bosutinib will be followed according to their usual management, estimated at every 3 months in conformity with recommendations of management of CML. Doctors will complete *via* eCRF a long-term follow-up visit for all these patients.

At this visit, the following information will be provided:

- Outcome of the CML Phase
- Therapeutic management of CML

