**Progression-free survival at 1, 2 and 3 years of patients treated with bosutinib:**

Progression-free survival will be defined as the duration between initiation of bosutinib and date of progression estimated by the participating doctor or death of patient (all causes combined) (Kaplan Meier method).

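### The phase-progression rule in section 9.7.3 conflicts with the visit schedule, the enrolled phases and the PFS definition, and should be reconciled before analysis

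*Protocol*

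**What the plan says.** The relevant text is spread over several places in the protocol.

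- **Section 9.7.3, Progression.** Phase progression is "Defined as passage from the chronic phase to the accelerated phase or to blast phase". The next sentence sets the confirmation rule: "This progression must be validated by two consecutive evaluations less than one week apart". A leukocyte criterion follows, to be met on a second measurement "and confirmed at least one week later". Loss of major haematological response is then listed, "with hematological confirmation within a time greater than or equal to 2 weeks after loss of initial response", and finally a cytogenetic criterion with no time interval.
- **Section 9.7.3, Progression-free survival.** PFS runs from initiation of bosutinib to the "date of progression estimated by the participating doctor or death of patient (all causes combined". The confirmation rule is not mentioned.
- **Section 9.1.** Follow-up visits are estimated at about every 3 months, and "No visit or additional examination will be requested by the protocol". Follow-up is left to the doctor's judgement.
- **Sections 9.2.1 and 4.** Chronic-, accelerated- and blast-phase patients are eligible. On survival, the synopsis says: "The percent survival will be estimated and described in each of the cohorts of interest".
- **Section 8.2.** PFS at 1, 2 and 3 years and the percent transforming to accelerated phase or blast crisis are named efficacy objectives.
- **Section 9.4.1.3.** After permanent discontinuation, the long-term visit lists two items: "Outcome of the CML Phase" and therapeutic management of CML.

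**The concern.** An endpoint definition has to be one that the planned data can satisfy, has to cover the patients it is applied to, and has to lead two analysts to the same event and date. This one has difficulty on each count.

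The one-week limit is a maximum gap, in a study whose routine gap is about 3 months. The starting state is chronic phase only, while accelerated-phase patients form a reporting cohort of their own. Two adjacent paragraphs give different routes to a progression event (confirmed evaluations, or the doctor's estimate) with no order of precedence.

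At stake are PFS at 1, 2 and 3 years and the percent transformation. Duration of response is also affected, because section 9.7.3 ends it at progression. Literal use of the rule can only remove progression events, so any error favours the product. If the choice between the two paragraphs is left until the data are in view, it becomes a post hoc choice.

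**Working it through.** **The plan's own figure.** The only design figure is the precision in section 9.5: a half-width of at most 10% with about 100 patients. At a 50% rate, 1.96 × √(0.25/100) = 0.098, or 9.8 points; Greenwood's formula at S = 0.5 with no censoring gives the same. The figure reproduces, and this point does not depend on it.

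**Timing.** Compare the confirmation rule with the intervals that the protocol describes:

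| Source | Interval | Within 7 days? |
|---|---|---|
| 9.7.3, phase criterion | less than 7 days (maximum) | – |
| 9.1, routine visits | about 3 months: 365.25/4 = 91 days | no |
| 7.3, ELN table, densest blood-count schedule | every 14 days until confirmed complete haematological response | no |
| 7.3, ELN table, after that response | at least every 3 months, or as needed | only if as-needed tests happen to fall there |

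On the routine schedule the phase criterion is not confirmed. Only unscheduled or as-needed evaluations can do it.

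**Direction.** The other two timed criteria in the same paragraph set minimum gaps (at least 7 days, at least 14 days). The phase criterion alone sets a maximum. A drafting or translation inversion is plausible, but an analyst following the text would apply the maximum.

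**Population.** Passage from accelerated to blast phase does not satisfy the phase criterion. The protocol gives no expected phase mix. If it resembled the study 200 table in section 7.3 (an assumption), the accelerated-phase share would be 76/(288 + 118 + 76 + 76) = 76/558 = 13.6%, or about 14 of 100 patients.

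**After discontinuation.** The long-term visit lists phase and therapy. Section 9.3 adds the last known responses at end of study, but that is not a serial record from which a confirmed loss of response can be read. On the listed items, the phase criterion carries most of the weight in these patients. The group may not be small: section 7.3 reports that about 20% stopped bosutinib after an adverse event in study 200.

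**Illustration of direction and size (all rates assumed).** Let progression occur at rate p, death without progression at d, death after progression at q, and let a share c of progressions be counted. A missed progression becomes an event only at death. Then

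PFS(t) = exp(−(p+d)t) + (1−c) × p × [exp(−qt) − exp(−(p+d)t)] / [(p+d) − q]

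With t = 3, d = 0.03, p = 0.08 and q = 0.50 per year:

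- the first term is exp(−0.33) = 0.719;
- the factor multiplying (1−c) is 0.08 × (0.223 − 0.719)/(0.11 − 0.50) = 0.102;
- all counted: 71.9%; half missed: 77.0%; all missed: 82.1%.

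Over p from 0.03 to 0.15 and q from 0.1 to 1.5 per year, with d fixed at 0.03:

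| p, q | all counted | half missed | all missed |
|---|---|---|---|
| 0.03, 1.5 (smallest shift) | 83.5% | 84.4% | 85.2% |
| 0.15, 0.1 (largest shift) | 58.3% | 73.1% | 87.9% |

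Missing half therefore raises 3-year PFS by about 1 to 15 points, and missing all by about 2 to 30. The shift is upward throughout. If the doctor's date governs and captures every progression, it is zero.

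**The case against.** There is a fair case that the text is less harmful than it looks.

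- **A reader might infer that the rule can never be met.** The documents do not support that. The rule asks for evaluations, not study visits; section 9.1 leaves follow-up to the doctor, and the ELN table allows counts as needed. A suspected transformation may well be re-examined within days. What stands is that the routine schedule does not provide this.
- **A reader might infer that PFS is overstated.** That is not established. The PFS paragraph uses the doctor's estimated date plus death from any cause. The two paragraphs can even be read together, one defining the event and the other saying who dates it. What stands is that precedence is unstated.
- **A reader might infer that accelerated-phase patients cannot progress.** They can: the leukocyte, haematological and cytogenetic criteria are not tied to a starting phase, and deaths count. The gap is confined to the phase criterion and the transformation percentage.
- **A reader might infer that progression cannot be assessed after discontinuation.** Section 9.4.1.3 lists two items but does not say they are the only ones. The synopsis says that follow-up data are collected independently of discontinuations, and the case report form is a separate document (Annex 1) that is not shown. What stands is that the protocol does not say which criteria apply there.
- **The analysis plan may settle it.** Section 9.7.3 leaves detail of the secondary objectives to the SAP, and section 9.7 lets the SAP change the protocol's plans. That makes the repair easy, but the definition stated in the protocol is still wrong as written.

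**Conclusion.** The point holds as an inconsistency in a stated endpoint definition. The confirmation interval does not fit the visit schedule and runs opposite to the other intervals in its paragraph. The phase criterion omits accelerated-to-blast passage in a study that enrols and reports accelerated-phase patients. The protocol does not say whether the confirmation rule applies to the PFS event.

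The consequence is conditional. If the Progression paragraph is applied literally, percent transformation is understated and PFS is biased upward. If the doctor's date governs and captures every progression, PFS is unaffected. The percent transformation has no separate definition in the protocol, so it stays exposed either way. The protocol states no progression rate and no share of progressions that would be confirmed in time, so the size of any bias cannot be derived from it; the ranges above rest wholly on assumed rates.

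This should be fixed, but it is not critical. The endpoints are secondary and descriptive, and the primary objectives (related adverse events and discontinuation because of them) are untouched.

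**What to change.** Before analysis, amend the analysis definition in section 9.7.3 and carry it into the SAP:

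1. Replace the one-week maximum by a minimum gap, or by confirmation at the next routine evaluation, and date the event at the first evaluation. This concerns how events are counted and asks for no extra visit or test.
2. Add passage from accelerated to blast phase as progression.
3. State whether the confirmed definition or the doctor's estimated date governs the PFS event, and report the other as a sensitivity analysis.
4. State which progression criteria count after permanent discontinuation, given the two items listed for the long-term visit.

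The cost is a few sentences and one extra PFS analysis. Under section 9.7 the SAP may change the protocol's plans, and an amendment is required only for major changes to the primary criteria and their analysis. The downside is that PFS may look slightly less favourable.
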